6.2.2 Intraoperative Photosensitivity Precautions

Reduced light settings and patient draping will be used to avoid potential problems from bright surgical lights, whenever possible. In addition, measuring oxygen saturation with pulse oximetry (pulse ox) exposes the skin to red light, which may cause skin burns if left in one place too long. When a pulse ox is used during neurosurgery, acute postoperative care and after approximately 30 days have elapsed (or as long as photosensitivity is experienced), care should be taken to have the photo detector/sensor device moved to a new location every few minutes. Use different fingers and toes if necessary. Continuous monitoring can be carried out by setting up multiple monitors and rotating on and off status of the fixed sensors, or by moving a single sensor to different pulsating arteriolar bed, such as the finger, great toe, nose, or earlobe.

6.3 Photofrin® Risks and Guidelines

6.3.1 Photosensitivity

The major risk of Photofrin® skin photosensitivity sensitivity, which will persist for some time after the procedure. Risks of photosensitivity can be avoided by taking light exposure

precautions. As such, all patients who receive Photofrin® will be instructed to avoid exposure of skin and eyes to direct sunlight or bright indoor light (from examination lamps, including dental lamps, operating room lamps, un-shaded light bulbs at close proximity, etc.) for at least 30 days. Some patients may remain photosensitive for up to 90 days or more. The photosensitivity is due to residual drug, which will be present in all parts of the skin.

6.3.2 Ocular Sensitivity

Ocular sensitivity to sun, bright lights, or car headlights, causing ocular discomfort, can occur in patients who receive Photofrin®. For at least 30 days and until ocular sensitivity resolves, patients will be instructed, to wear dark sunglasses when outdoors. Sunglasses have an average white light transmittance of < 4% and will reduce risk of ocular sensitivity.

6.3.3 Photobleaching Precautions

Exposure of the skin to ambient indoor light is, however, beneficial because the remaining drug will be inactivated gradually and safely through a photobleaching reaction. Therefore, patients should not stay in a darkened room during this period and should be encouraged to expose their skin to ambient indoor light. The level of photosensitivity will vary for different areas of the body, depending on the extent of previous exposure to light. Before exposing any area of skin to direct sunlight or bright indoor light, the patient should test it for residual photosensitivity. A small area of skin should be exposed to sunlight for 10 minutes. If no photosensitivity reaction (erythema, edema, blistering) occurs within 24 hours, the patient can gradually resume normal outdoor activities, initially continuing to exercise caution and gradually allowing increased exposure. If some photosensitivity reaction occurs with the limited skin test, the patient should continue precautions for another 2 weeks before retesting. The tissue around the eyes may be more sensitive, and therefore, it is not recommended that the face be used for testing. If patients travel to a different geographical area with greater sunshine, they should retest their level of photosensitivity. Conventional ultraviolet (UV) sunscreens will only protect against UV light-related photosensitivity and will be of no value in protecting against induced photosensitivity reactions caused by visible light.

6.3.4 Use Before or After Radiotherapy

If PDT is to be used before or after radiotherapy, sufficient time should be allotted between the two therapies to ensure that the inflammatory response produced by the first treatment has subsided before commencing the second treatment. The inflammatory response from PDT will depend on tumor size and extent of surrounding normal tissue that receives light. It is recommended that 2 to 4 weeks be allowed after PDT before commencing radiotherapy. Similarly, if PDT is to be given after radiotherapy, the acute inflammatory reaction from radiotherapy usually subsides within 4 weeks after completing radiotherapy, after which PDT may be given.

6.3.5 Hepatic and Renal Impairment

Hepatic or Renal impairment will likely prolong the elimination of porfimer sodium leading to higher rates of toxicity. Patients with severe renal impairment or mild to severe hepatic impairment should be clearly informed that the period requiring the precautionary measures for photosensitivity may be longer than 90 days.

6.3.6 Thromboembolism

Thromboembolic events can occur following photodynamic therapy with Photofrin®. Most reported events occurred in patients with other risk factors for thromboembolism including advanced cancer, following major surgery, prolonged immobilization, or cardiovascular disease.

6.3.7 Pulse Oximetry Use Precautions

In addition, the use of pulse oximetry (pulse ox) exposes the skin to red light, which may cause skin burns if left in one place too long. Up to 30 days or as long as photosensitivity is experienced, after receive Photofrin®, care should be taken to have the photo detector/sensor device moved to a new location every few minutes. Use different fingers and toes if necessary. Continuous monitoring can carried out by setting up multiple monitors and rotating on and off status of the fixed sensors, or by moving a single sensor to different pulsating arteriolar bed, such as the finger, great toe, nose, or earlobe.

6.4 Overall Adverse Reaction Profile

Systemically induced effects of photodynamic therapy (PDT) with Photofrin® consist of photosensitivity and mild constipation. All patients who receive Photofrin® will be photosensitive and must observe precautions to avoid sunlight and bright indoor light. Photosensitivity reactions occurred in approximately 20% of cancer patients and in 69% of high-grade dysplasia (HGD) in Barrett's esophagus (BE) patients treated with Photofrin®. Typically these reactions were mostly mild to moderate erythema but they also included swelling, pruritus, burning sensation, feeling hot, or blisters. In a single study of 24 healthy subjects, some evidence of photosensitivity reactions occurred in all subjects. Other less common skin manifestations were also reported in areas where photosensitivity reactions had occurred, such as increased hair growth, skin discoloration, skin nodule, skin wrinkling and increased skin fragility. These manifestations may be attributable to a pseudoporphyrin state (temporary drug-induced cutaneous porphyria).

In the Australian study conducted in 136 adult patients, there were no direct serious complications from the PDT itself. One patient died from acute myocardial infarction and another suffered a hemiplegia (total paralysis of the arm, leg, and trunk on the same side of the

body) after tumor resection. Three patients had increasing drowsiness (somnolence) and hemiparesis (muscle weakness on only one side of the body) associated with cerebral edema (excess accumulation of water in the brain) despite usual doses of steroid. All three cases resolved after the use of steroids and diuretics.

In the US pediatric and adult study, two out 20 patients developed complications. Immediately postoperatively, one patient developed severe truncal ataxia (lack of muscle coordination), bilateral facial weakness as well as dysphagia (difficulty swallowing). The other patient who underwent an extensive reoperation followed by laser light PDT, had a right facial nerve palsy (paralysis), which improved in 3 months, but did not completely resolve.

6.5 Phlebotomy Risks

Inserting a needle for blood sampling can be associated with some discomfort and bruising and, although very rarely, inflammation of the arm veins or possible infection.

Infusion reactions: Infusion reactions including urticaria, bradycardia, hypotension, dizziness, and hypertension

6.6 Post-Marketing Experience

The following adverse reactions have been identified during post-approval use of Photofrin® with PDT. Because these reactions are reported voluntarily from a population of uncertain size, it is not always possible to reliably estimate their frequency or establish a causal relationship to drug exposure.

6.7 Concurrent Anticancer Therapy

Concurrent anticancer therapy not defined within this protocol, including chemotherapy, radiation therapy, immunotherapy, or biologic therapy may NOT be administered to patients receiving study drug (from Day -30 to Day +30). If anticancer therapeutics are administered to the patient during this time he or she may (1) not be permitted to begin protocol therapy, (2) be removed from protocol therapy, (3) be considered inevaluable for toxicity review and/or survival analyses.

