3.5 Patients Who Do Not Begin Study Treatment

If a patient is registered on the study, and is later found not able to begin the planned study treatment, for whatever reason, the patient will be removed from study and treated at the physician's discretion. Study data will be collected until the time of study removal. The reason for removal from study will be clearly indicated on the case report forms.

If a patient begins treatment, and then is discontinued for whatever reason, the patient must be followed for 3 months for toxicity review.

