5.3 Modifications For Toxicities

There will be no dose modifications for the administration of Photofrin®. All enrolled patients will receive 2.5 mg kg⁻¹. If the enrolled patient does not receive the full investigation drug dose or complete the intraoperative photodynamic therapy for any reason, the patient should be evaluated for toxicities for 90 days. The patient must follow the precautions and consideration of Photofrin® risks.

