10.2 Sample Size and Study Duration

The sample size is based on a single-arm phase II study designed to detect an increase in the 6-month relapse-free survival rate from the historical value of 35% (treated as fixed) to 55%. With 29 subjects with known 6-month outcome, the study will have 80% power to detect such an increase at a one-sided 10% significance level. This calculation is slightly conservative, because

it does not incorporate the increase in the estimated survival rate from censored observations, thus the actual power might be slightly higher. A censoring rate of less than 5% is expected, so 30 patients will be enrolled in the study. The following table shows the estimated power of the study under various hypothetical values of 6-month relapse-free survival.

6-month RFS	Power
45%	43%
50%	64%
55%	82%
60%	93%
65%	98%

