10.3 Methods of Analysis

Survival probabilities will be estimated by using the product limit estimate technique. Overall survival and Relapse-free survival will be visualized using Kaplan-Meier plots. Greenwood's formula will be used to estimate the variance. The 6-month relapse free survival will be compared to the historical control value of 35% via a one-sided z-test at a 10% significance level.

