4. Progression will be defined by any of the following: > 25% increase in sum of the products of perpendicular diameters of enhancing lesions compared with the smallest tumor measurement obtained either at baseline (if no decrease) or best response, on stable or increasing doses of corticosteroids; significant increase in T2/FLAIR nonenhancing lesion on stable or increasing doses of corticosteroids compared with baseline scan or best response after initiation of therapy not caused by comorbid events (e.g., radiation therapy, demyelination, ischemic injury, infection, seizures, postoperative changes, or other treatment effects); any new lesion; clear clinical deterioration not attributable to other causes apart from the tumor (e.g., seizures, medication adverse effects, complications of therapy, cerebrovascular events, infection, and so on) or changes in corticosteroid dose; failure to return for evaluation as a result of death or deteriorating condition; or clear progression of nonmeasurable disease.

These criteria are published and currently accepted in the neuro-oncology community⁵⁸. The imaging interpretation will be completed by a board certified neuro-radiologist, while the neurological outcome/status will be assessed by a board certified neurologist/neuro-oncologist.

PDT Phase II Trial – Glioma Tumors In Adults

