12.6.1 Additional Protocol Specific Reporting Requirements

12.6.1 Reporting to the Medical College of Wisconsin/Froedtert Hospital IRB

The Principal Investigator will submit timely reports to the MCW/FH IRB including any unanticipated problems, serious adverse device and drug events occurring during the investigation, and any deviation from the investigational plan, either unintentional or made to protect the life or physical wellbeing of a subject in an emergency. Any UPIRSO's, Internal Adverse Events, Adverse Device or Drug Effects, or other events meeting the MCW/FH IRB prompt reporting criteria will be reported no later than 5 calendar days after the study team becomes aware of the problem, event or information. All other adverse events will be reported at time of continuing review in accordance with MCW/FH IRB policy. Non-serious Adverse Events (collected from Day 0 to Day +30/1-Month follow-up) and non-serious/administrative protocol deviations will be collected and reported on an annual basis as per MCW/FH IRB policy. SAEs (collected from Day 0 to Day +90) that are unrelated to the study will be reported to the IRB on an annual basis via the DSMC Study progress reports. Refer to section 13.3 for details. SAEs require DSMC expedited review will be reported to the IRB within 5 calendar days.

12.6.2 Reporting to Pinnacle Biologics, Inc.

The industry collaborator, Pinnacle Biologics, Inc. is an international company with obligations in several European countries to quickly report all SAEs from all ongoing clinical trials using Photofrin®. We have developed a reporting plan that will facilitate Pinnacle's reporting requirements while safeguarding patient's confidentiality.

Reporting Serious AEs:

The investigator will report each SAE, regardless of causality, within 24 hours of awareness by

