13.3.2 Expedited Reporting to the Data Safety Monitoring Committee

SAEs that will be assessed for trial monitoring/stopping are defined as any of the following events with possible attribution to the experimental intervention(s) (the investigational drug,

investigational device, and/or investigational therapy). This study will utilize version 4.0 of the CTCAE of the National Cancer Institute (NCI) for toxicity and performance reporting. A copy of the CTCAE version 4.0 can be downloaded from the CTEP website. Additionally, toxicities are to be reported on the appropriate case report forms.

Please note: 'CTCAE v4.0' is understood to represent the most current version of CTCAE v4.0 as referenced on the CTEP website (ie, v4.02 and all subsequent iterations prior to version 5.0). The DSMC will be notified within 5 calendars days of all serious adverse events occurring within 30 days after receipt of protocol therapy, which meets the criteria of one or more of the following:

Monitoring of Serious Adverse Events for Stopping Guidelines

1. Photosensitivity:

Skin changes of Grade 4 or higher occurring within 4 weeks of Photofrin® injection.

2. Ocular Sensitivity:

Photophobia of Grade 4 or greater occurring within 4 weeks of Photofrin® injection.

3. Neurotoxicity:

Attributing a measured decline in neurologic status to either resection or PDT will be difficult as many patients have deficits from surgical resection alone. In addition, many patients have significant neurological changes immediately post-op that improve with time and steroids. These transient neurological deficits are believed to be secondary to acute tissue injury followed by inflammation. Most transient neurological deficits improve within the first month post-op, while fixed deficits do not. Fixed deficits have a greater impact on overall quality of life. For the purposes of this study neurotoxicity will be defined as persistent neurological deficits measured at 4 weeks of Grade 4 or greater, or a decline of 2 levels (i.e. 1 to 3) when compared to pre-operative testing, recorded baseline toxicities. The study team will attempt to localize deficiencies using MRI, clinical exams and other testing (i.e. EEG) to the brain outside of the resection, but within the penumbra of the photodynamic effect (within 2 cm of the surgical field) to help with attribution (surgery versus PDT) when possible.

4. Any other hematologic or non-hematologic toxicity Grade 4 or higher.

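### Section 6.7 lets patients given outside anticancer therapy by Day +30 be ruled out of survival analyses at discretion, and Section 10 names no primary analysis set, so early failures could leave the 6-month RFS test

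*Combined protocol and SAP*

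**What the plan says.** Section 6.7 prohibits anticancer therapy not defined in the protocol from Day -30 to Day +30. It lists three possible consequences if such therapy is given; the third is that the patient may "be considered inevaluable for toxicity review and/or survival analyses". The rule is permissive and names no criterion, no decision-maker and no timing relative to outcome.

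Section 10.3 estimates overall survival and RFS by the product-limit method with Greenwood's variance. The 6-month RFS "will be compared to the historical control value of 35% via a one-sided z-test at a 10% significance level". The primary endpoint is therefore one of the survival analyses that 6.7 refers to.

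No part of Section 10 defines an intention-to-treat, treated or evaluable set. The 29 patients with known outcome in 10.2 are an input to the power calculation. Section 10.4 mentions later therapy only for secondary objectives, after a sustained response. Section 9.1 keeps patients who are off protocol therapy in follow-up but does not say that they are analysed. Section 5.3 foresees a patient who "does not receive the full investigation drug dose or complete the intraoperative photodynamic therapy for any reason" and asks for 90 days of toxicity evaluation. Section 3.5 says, for a patient who starts and then stops treatment, that "the patient must be followed for 3 months for toxicity review". Neither says whether such a patient counts in the RFS analysis.

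**The concern.** A rule that removes patients after treatment, at discretion, is harmless only if removal is unrelated to outcome. Here a relation is plausible. A patient who progresses in the first month is a natural candidate for further therapy. Progression could be found on the Week +4 MRI, on an earlier clinically indicated MRI, or clinically: Section 11.3 accepts "clear clinical deterioration not attributable to other causes apart from the tumor" as progression. If that patient then receives outside therapy before Day +30, 6.7 allows a known failure to leave both numerator and denominator.

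The trial is open and has no control arm in which the same exclusion would operate, and the comparison value is fixed at 35%. Selective loss of failures would raise the RFS estimate and the false-positive rate. With no stated primary set, a reader of the results could not tell whether this had happened.

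Only the part of the window after Photofrin matters here. Therapy between Day -30 and Day 0 cannot be a response to relapse after treatment.

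**Working it through.** **Inputs from the documents.** Null 35%, target 55%, one-sided 10%, 29 known outcomes, 30 enrolled (10.2); z-test with Greenwood variance (10.3), which without censoring is p(1-p)/n, the Wald form; window closing at Day 30 (6.7).

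**Assumptions, not in the documents.** Constant hazard, six months = 182.6 days, no censoring, a gap g of 14 or 21 days from progression to outside therapy, and a share f of the affected failures dropped.

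**1. The plan's own figure.** Exact binomial, n = 29, success at 14 or more: type I error 9.8%. Power is 43.1%, 64.4%, 82.0%, 92.9% and 97.9% at true RFS of 45%, 50%, 55%, 60% and 65%. This matches the table in 10.2 (43, 64, 82, 93, 98%). The sample size is not in error.

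**2. Who could be affected.** Progression must occur by Day 30 - g, so the share is a = 1 - 0.35^((30-g)/182.6).
- g = 14: 1 - 0.35^(16/182.6) = 0.088, or 2.6 of 30.
- g = 21: 1 - 0.35^(9/182.6) = 0.050, or 1.5 of 30.
- g = 0: 1 - 0.35^(30/182.6) = 0.158, an upper case only.

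**3. Effect of dropping them.** Let e = f × a. Apparent RFS is 0.35/(1-e). The number excluded, K, is Binomial(30, e). Type I error is the sum over K of P(K) × P(X ≥ c), with X Binomial(30-K, 0.35/(1-e)) and c the Wald critical count: 15 of 30, 14 of 29, 14 of 28, 13 of 27, and so on. The comparator uses the same e but keeps success probability 0.35, that is, the same loss unrelated to outcome.

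| Gap | Share dropped | Apparent RFS | Type I error | Same loss, unrelated to outcome | Excess (points) |
|---|---|---|---|---|---|
| 14 days | 25% | 35.8% | 9.3% | 7.9% | 1.4 |
| 14 days | 50% | 36.6% | 11.7% | 8.5% | 3.2 |
| 14 days | 100% | 38.4% | 17.0% | 9.2% | 7.8 |
| 21 days | 25% | 35.4% | 8.2% | 7.4% | 0.8 |
| 21 days | 50% | 35.9% | 9.6% | 8.0% | 1.7 |
| 21 days | 100% | 36.9% | 12.4% | 8.6% | 3.8 |

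The excess is taken before rounding.

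**4. Why the excess is the figure to use.** With 14 of 30, the Wald statistic is (0.4667 - 0.35)/√(0.4667 × 0.5333/30) = 1.2809, against a cut-off of 1.2816: a miss by 0.0007. With the null variance, 14 of 30 passes (z = 1.34). With nobody excluded, the exact error is therefore 6.5% under Wald and 12.6% under the null variance. Whether a scenario crosses 10% depends on this near-tie. Repeating step 3 with c = 14 for n = 30 (the other counts listed above do not change) gives an excess of 3.6 or 8.0 points (14 days) and 2.1 or 4.2 points (21 days) for half or all dropped, close to the Wald figures.

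An example that does not depend on the variance form: 13 of 30 gives z = 0.92 (Wald) or 0.96 (null variance), not significant. The same 13 after three early failures are removed, 13 of 27, gives 1.37 or 1.43, significant.

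**5. The opposite direction.** The chance of being relapse-free at six months, given progression-free at Day 30, is 0.35/0.8416 = 0.416. Excluding a share e of all patients from that group gives (0.35 - 0.416e)/(1-e) = 34.8%, 34.5% or 34.3% for 1, 2 or 3 of 30.

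**The case against.** The strongest reply is that the effect is likely to be small. The therapy is prohibited in the window, exclusion is only permitted, and no number is given. The 14-day scenario needs 8.8% of patients to progress by Day 16 after maximal resection. The Week +4 scan falls at Day 25 to 31, so progression dated by that scan leaves at most five days before Day 30 and fits neither assumed gap. The model also treats every early failure as someone who could go on to therapy, although some would be deaths. At 25% dropped, apparent RFS rises by only 0.8 or 0.4 points. All of this stands and limits the size of the concern. It does not remove a stated rule that can act on outcome.

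Several stronger readings are tempting but unsupported:

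- A reader might infer that progression before Week +4 can only be called clinically, and that 13.3.2 concedes this is unreliable where it says that "many patients have significant neurological changes immediately post-op that improve with time and steroids". Sections 5.1.6 and 5.1.7 and Appendix 1 allow clinically indicated MRI earlier. The 13.3.2 text concerns attributing deficits to resection or to PDT, not recognising progression.
- A reader might infer a loss of power, because 10.2 says: "A censoring rate of less than 5% is expected, so 30 patients will be enrolled in the study". Under the Wald counts, exact power at 55% is 76.9% for n = 30, 82.0% for n = 29 and 76.5% for n = 28. One or two exclusions do not produce a meaningful loss.
- A reader might see a conflict between Week +4 in 5.1.7 and "Day +30/1-Month follow-up" in 12.6.1. The latter concerns adverse-event collection, and Week +4 ±3 days contains Day 30.
- False-positive rates of 22.0% or 34.5% follow only if three or four, or five, early failures of 30 are all deleted. Nothing in the documents points to that many.

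**Conclusion.** The gap is real and should be fixed, but its likely effect is modest. Section 6.7 permits a discretionary exclusion from the primary analysis that can depend on outcome, and nothing in Section 10 overrides it. If half or all of the affected early failures were dropped, the type I error would exceed that from an outcome-unrelated loss of the same size by 3.2 or 7.8 points (14-day gap), or by 1.7 or 3.8 points (21-day gap). These figures rest on an assumed constant hazard, true RFS of 35%, no censoring and assumed gaps; the documents supply none of these as facts about the excluded patients. The bias is possible rather than certain, and its direction depends on who is excluded. The documents do not support a claim that the trial will be biased, or that its size or power is wrong.

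**What to change.** In 6.7, delete the words that extend inevaluability to survival analyses. In 10.3, add wording to this effect:

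- The primary 6-month RFS analysis includes all treated patients, whether or not they received outside therapy. Progression or death before that therapy counts as an event.
- Any exclusion or censoring under 6.7 is a sensitivity analysis only, with the number and reasons reported.
- Patients given Photofrin but not illuminated are listed with reasons and outcomes and added in a sensitivity analysis. This matters because 10.1 places a frozen-section discussion between dosing and activation, so a set limited to illuminated patients is itself a post-dosing selection that should be visible.

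The cost is wording, with no new visits. Section 9.1 already requires follow-up of patients off protocol therapy, and Appendix 1 schedules disease evaluation and survival status at Week 24. The downside is that the estimate may be slightly less favourable and that later therapy remains part of the primary result.

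Separately, the Day +30 limit in 6.7 and the 2 to 4 weeks before radiotherapy in 6.3.4 do not agree: a patient treated in line with 6.3.4 could be ruled inevaluable under 6.7. The sponsor should reconcile the two; no view is taken here on which is right.

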5.1.3 Preoperative Administration of Photofrin®

The subjects entering the study will receive a prescribed dose of 2.5 mg kg^{-1} of Photofrin® (supplied by Pinnacle Biologics, Inc., Bannockburn, IL), given intravenously over 3-5 minutes during an outpatient clinic visit, scheduled 24 hours prior to the planned surgical resection. Research participants will report to the Adult Translational Research Unit (TRU) to receive the injection by a TRU nurse. Prior to the administration of Photofrin® the TRU nurse will assess the patient and ensure the patient has adequate protective gear and clothing for the patient's journey home and back to the hospital for tumor resection the following day. Subjects will have already received a PDT Patient Kit and instructions for protection from sunlight. Subjects will be advised to remain out of direct sunlight and bright artificial lighting for at least 30 days and up to 90 days after Photofrin® injection and PDT. (Appendix 2) If a photosensitivity reaction occurs, subjects are instructed to contact their physician immediately for guidance in the treatment of the reaction.

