9.0 CRITERIA FOR REMOVAL FROM PROTOCOL THERAPY AND OFF STUDY CRITERIA

9.1 Criteria for Removal from Protocol Therapy

1. Refusal of further protocol therapy by patient/legally authorized representative
2. Physician determines it is in patient's best interest.
3. Patient becomes pregnant while on study.

Patients who are off protocol therapy are to be followed until they meet the criteria for Off Study (see below). Follow-up data will be required unless consent was withdrawn.

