13.3.4 Safety Monitoring and Stopping Guidelines

To ensure the safety of patients on study, SAEs will be reported by 4 Weeks post PDT as defined in section 13.3.1 or section 13.3.2. The 6-month relapse free survival status will be determined based on radiological assessment as defined by section 11 and standard of care medical exam carried out at Week +24. Expected enrollment is 30 patients over the course of 3 years. The stopping guidelines are summarized in the table below.

Table: Stopping Guideline for Dose Limiting Toxicities or 6-month Relapse Free Survival

Number of patients (n)	Stopping boundary (x)
1-6	2
7-12	3
13-18	4
19-30	5

** Stopping guideline is triggered if $\geq x$ patients out of n experience a SAE with attribution to the protocol*

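### Section 6.7(3) allows a patient already exposed to Photofrin and light to be ruled inevaluable for toxicity, and with no safety population defined it could be read to take that patient out of the 13.3.4 count

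*Combined protocol and SAP*

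**What the plan says.** Section 6.7 states that outside anticancer therapy "may NOT be administered to patients receiving study drug (from Day -30 to Day +30"). If it is given, three consequences may follow. The patient may not be permitted to start, may be removed from protocol therapy, or may "be considered inevaluable for toxicity review and/or survival analyses".

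Exposure comes early in that window. Section 5.1.3 has Photofrin "scheduled 24 hours prior to the planned surgical resection", and the table in 5.1.1 puts drug on Day 0 and light on Day 1.

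Three other sections deal with patients who stop:

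- Section 3.5: "If a patient begins treatment, and then is discontinued for whatever reason, the patient must be followed for 3 months for toxicity review".
- Section 9.1: "Patients who are off protocol therapy are to be followed until they meet the criteria for Off Study".
- Section 5.3: a patient who "does not receive the full investigation drug dose or complete the intraoperative photodynamic therapy for any reason" comes under the rule that "the patient should be evaluated for toxicities for 90 days".

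The table in 13.3.4 is the only numeric safety boundary. Its guideline is reached when at least x "patients out of n experience a SAE with attribution to the protocol". The table does not say whether n means enrolled, treated or evaluable patients. The document defines neither the term inevaluable nor a safety population.

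**The concern.** Exposure to drug and light cannot be undone by later therapy, so a toxicity analysis would normally keep every exposed patient. Section 6.7(3) permits the opposite. It says *may*, and names neither who decides nor when. The trial is open-label and single-arm, and 13.3.2 assesses persistent neurological deficit at 4 weeks, which lies inside the Day +30 window. The ruling could therefore be made with the event already known.

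Two things are at stake. One is the chance that the pre-set boundary prompts a DSMC consultation. The other is whether the descriptive safety report under objective 1.2.1 rests on all exposed patients or on a chosen subset.

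**Working it through.** **1. Does 6.7 reach exposed patients?** Yes. The window runs to Day +30, and drug and light are given on Days 0 and 1.

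**2. Can a patient who follows the other sections fall inside the window?** Yes.
- Section 4.1 allows entry 3 weeks (21 days) after chemotherapy and 4 weeks (28 days) after radiotherapy. Both are shorter than 30 days, so the overlap arises when enrolment is close to Day 0.
- Section 6.3.4 recommends 2 to 4 weeks (14 to 28 days) between PDT and radiotherapy. With PDT on Day 1 that is Day +15 to Day +29, before Day +30.

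**3. Which passages pull against 6.7(3)?**
- Section 3.5 applies to a patient removed under 6.7(2). That patient must have three months of toxicity review, yet may be inevaluable for toxicity review. The two sections use the same term.
- Section 9.1 keeps the patient in follow-up after therapy ends.
- Section 5.3 applies only if drug or light was incomplete. A patient who completed both is outside it, so it is not a direct contradiction.

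**4. What could removal do to the boundary?** The plan gives no unacceptable rate or trigger probability for the table, so there is no stated figure to reproduce.

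Inputs from 13.3.4: x = 2 for n of 1-6, 3 for 7-12, 4 for 13-18, 5 for 19-30; 30 patients. Assumptions, because the documents give neither: true attributed-SAE rate p, and share q of event patients ruled inevaluable.

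Method: an exact recursion on the state (counted n, counted x), checked after each patient. A patient with an event is counted with probability p(1 - q). A removed event patient is either kept in n as a non-event or dropped from n and x, and the ranges below cover both.

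Hand check of the first block, p = 20%, q = 0. The chance of 2 or more events in 6 patients is 1 - 0.8^6 - 6 × 0.2 × 0.8^5 = 1 - 0.2621 - 0.3932 = 34.5%. With q = 20% and removed patients kept in n, the counted rate is 0.2 × 0.8 = 16%. The same formula gives 1 - 0.3513 - 0.4015 = 24.7%.

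Chance of triggering by 30 patients:

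| Share of event patients removed | p = 15% | p = 20% |
|---|---|---|
| none | 55.7% | 79.3% |
| 10% | about 47% | about 71% |
| 20% | 38-39% | 61-62% |
| one third | 26-27% | 46-48% |

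If removal is unrelated to events and takes 10% or 20% of all patients out of both n and x, the 79.3% at p = 20% becomes 73.1% or 67.3%.

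In patients: for n of 19-30, four counted events do not trigger (x = 5). Each removed event patient adds one to the number that can occur without a trigger.

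**The case against.** **The DSMC sees the events anyway.** Section 13.3.2 sends qualifying SAEs to the DSMC within 5 days, with no evaluability condition. The semi-annual report in 13.3.1 contains all SAE reports and a patient listing. Under 13.3.3 the boundary prompts consultation and does not close enrolment. This stands, and it limits the harm to the pre-set trigger and the denominator of the safety report.

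**No passage removes anyone from x or n.** This also stands. The 13.3.4 footnote, read alone, counts every patient with an attributed SAE. A reader might infer that 6.7 does drop events from the boundary, but the text supports only that it could be read so, because n and evaluability are undefined.

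**Follow-up and evaluability differ.** A patient can be followed for three months and still be judged confounded. That is why this is a tension with 3.5 and 9.1 and not a flat contradiction. The shared term leaves it unresolved.

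**Selection is not documented.** A reader might infer that early outside therapy marks patients who are declining and more likely to have neurological events. No passage says so. Section 5.1.7 speaks of further therapy after recovery from surgery, which could equally select fitter patients. For that reason the working also gives removal unrelated to events.

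**Conclusion.** The point holds as a gap in definition joined to a rule that should not apply to exposed patients. Section 6.7(3) literally permits an exposed patient to be ruled inevaluable for toxicity, and nothing in 13.3.4 or elsewhere prevents that ruling from reaching the count. At an assumed true rate of 20%, the loss in trigger probability runs from about 6 percentage points (10% of all patients removed regardless of events, 79.3% to 73.1%) to about 33 (one third of event patients removed, 79.3% to 46%). Event rates and removal shares are assumptions throughout, so the table shows sensitivity and does not forecast.

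The documents do not support saying that SAEs would be hidden from the DSMC, or that 5.3 is contradicted. The change is worth making because it costs little, and because boundaries of 2 to 5 patients are sensitive to a single omission.

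**What to change.** 1. In 6.7(3), delete the words *toxicity review and/or*.
2. State that every patient who received any Photofrin stays in the safety set and in n of the 13.3.4 table. Such a patient counts in x if an attributed SAE meeting 13.3.2 occurs within the counting window already given in 13.3.2 and 13.3.4. The window should not be stretched to the three-month follow-up, because that would change how often the boundary triggers.
3. Record outside therapy and its start date, and weigh them when attributing an event, without removing the patient.
4. Reconcile the Day -30 to Day +30 window in 6.7 with the intervals in 4.1 and 6.3.4. Which interval is right is for the sponsor.

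Cost: protocol wording only, with no change to the sample size or the boundary. Some counted events will be harder to attribute, a difficulty that 13.3.2 already accepts for surgery versus PDT.
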